8.1.2. Ibrutinib

Ibrutinib will be supplied by Celgene and labeled appropriately as investigational material for the study. Ibrutinib is supplied as 140 mg capsules. The recommended dose of ibrutinib for subjects with CLL according to the ibrutinib package insert or SmPC ([IMBRUVICA](#)) is 420 mg (three 140 mg capsules) orally once daily. Refer to Section [8.2.2.2](#) for administration information.

Celgene will continue to provide an investigational supply of ibrutinib for ongoing patients experiencing clinical benefit, for up to 24 cycles of CC-122. For patients who discontinue CC-122 prior to 24 cycles or if patients have surpassed the 24 cycles of CC-122, Celgene will continue to provide an additional 3 cycles of ibrutinib from the investigational supply to allow time for patients to be switched to commercially available ibrutinib and/or other therapies at the discretion of the treating physician.

Refer to the Pharmacy manual, package insert, or SmPC for stability and storage information.

8.1.3. Obinutuzumab

Obinutuzumab will be supplied by Celgene and labeled appropriately as investigational material for the study.

Refer to the obinutuzumab IB, package insert or SmPC ([GAZYVA, GAZYVARO](#)) for preparation and administration information. Refer to Section [8.2.2.3](#) for timing of obinutuzumab administration. Premedicate according to the PI, SmPC, or institutional standards.

Recommended premedications will be provided by the investigational site. The sponsor will not provide these medications.

Obinutuzumab is to be administered only as an intravenous (IV) infusion.

Celgene will continue to provide the protocol-specified total of 6 cycles of investigational supply of obinutuzumab for ongoing patients experiencing clinical benefit. In the event CC-122 is discontinued prior to obinutuzumab, subjects may continue to receive the protocol-specified total of 6 cycles of obinutuzumab at the discretion of the treating physician. In addition, for patients that have surpassed the 24 cycles of CC-122, Celgene will continue to provide an additional 3 cycles of CC-122 to allow time for patients to be switched to commercially available therapies at the discretion of the treating physician.

Refer to the Pharmacy manual, PI, or SmPC for stability and storage information.

8.1.4. Premedications

Other recommended medications such as allopurinol will be provided by the investigative site. The sponsor will not provide these medications.

Please refer to Section [9.3.3](#) for required premedications for obinutuzumab infusions.

8.2. Treatment Administration and Schedule

As of 05 Jul 2018, enrollment of new subjects into Phase 1 has been discontinued and Phase 2 will not proceed.

CC-122-CLL-001 is a Phase 1/2 open-label, dose finding study evaluating CC-122 administered orally to subjects with CLL/SLL. Subjects who are eligible for the study will be assigned to one of the following arms:

- **Arm A:** CC-122 single agent
- **Arm B:** CC-122 in combination with ibrutinib
- **Arm C:** CC-122 in combination with obinutuzumab

Cycle 1 Day 1 treatment may begin if the following parameters are met:

- All eligibility criteria
- The ANC is $\geq 1,500$ cells/mm 3 ($1.5 \times 10^9/L$) or $\geq 1,000$ cells/mm 3 ($1.0 \times 10^9/L$) if secondary to bone marrow involvement by disease
- The platelet count is $\geq 100,000$ cells/mm 3 ($100 \times 10^9/L$) or $\geq 50,000$ cells/mm 3 ($50 \times 10^9/L$) if secondary to bone marrow involvement by disease
- AST/ALT $< 3 \times$ ULN

8.2.1. Safety Review Committee

Safety considerations, including decisions to open a new dose level cohort will be made by an SRC. The SRC membership will be comprised of the sponsor's medical monitor and drug safety physician, the lead coordinating investigator (or designee), European coordinating investigator (or designee) and 2 additional physicians participating in the study and nominated by the coordinating investigators as having sufficient prior experience in early phase studies in CLL and in the use of lenalidomide in CLL. Other study team members (eg, study statistician) may also participate in SRC meetings as needed. Discussions and outcomes of SRC meetings will be documented and provided to all study investigators.

8.2.2. Dose Escalation Phase

8.2.2.1. Arm A: CC-122 Single Agent

Subjects assigned to Arm A will be administered a starting dose of 1.0 mg CC-122 orally on a 5/7-day (5 continuous days out of 7 days per week) schedule starting at Cycle 1 Day 1 with intrasubject dose escalation every 2 weeks at 0.5 mg increments at the discretion of the investigator as tolerated up to a maximum dose of 4.0 mg for a total of 24 cycles of CC-122, or until disease progression, unacceptable toxicity or discontinuation for any other reason, whichever is earlier. All treatment cycles are 28 days. Each dose will be taken in the morning with about 8 ounces of water. CC-122 may be taken up to 12 hours late if dosing has been delayed on a single day; otherwise that day's dose should be omitted.

8.2.2.2. Arm B: CC-122 in Combination with Ibrutinib

Subjects in Arm B will be administered CC-122 orally on a 5/7-day schedule. CC-122 will be initiated on Cycle 2 Day 1 and on Day 1 of each cycle thereafter up to a maximum of 24 cycles of CC-122, or until disease progression, unacceptable toxicity or discontinuation for any other reason, whichever is earlier. Each dose will be taken in the

morning with about 8 ounces of water. CC-122 may be taken up to 12 hours late if dosing has been delayed on a single day; otherwise that day's dose should be omitted.

Dosing of ibrutinib is as described in the [IMBRUVICA](#) package insert or SmPC. Subjects will take orally three 140 mg capsules of ibrutinib daily for a total daily dose of 420 mg. Ibrutinib should be taken once daily at approximately the same time each day. The capsules should be swallowed whole with water and subjects should not open, break or chew capsules. Ibrutinib will be administered daily starting Cycle 1 Day 1 up to a maximum of 24 cycles of CC-122, or until disease progression, unacceptable toxicity or discontinuation for any other reason, whichever is earlier. For patients who discontinue CC-122 prior to 24 cycles or if patients have surpassed the 24 cycles of CC-122, Celgene will continue to provide an additional 3 cycles of ibrutinib from the investigational supply to allow time for patients to be transitioned to commercially available ibrutinib and/or other therapies at the discretion of the treating physician. Toxicity-related dose interruptions and modifications for ibrutinib are described in Section [8.2.12.2](#).

8.2.2.3. Arm C: CC-122 in Combination with Obinutuzumab

Subjects in Arm C will be administered CC-122 orally on a 5/7-day schedule.

CC-122 will be initiated on Cycle 1 Day 9 and on Day 1 of each cycle thereafter up to a maximum of 24 cycles of CC-122, or until disease progression, unacceptable toxicity or discontinuation for any other reason, whichever is earlier. Each dose will be taken in the morning with about 8 ounces of water. CC-122 may be taken up to 12 hours late if dosing has been delayed on a single day; otherwise that day's dose should be omitted.

Celgene will continue to provide the protocol-specified total of 6 cycles of investigational supply of obinutuzumab for ongoing patients experiencing clinical benefit. In the event CC-122 is discontinued prior to obinutuzumab, subjects may continue to receive the protocol-specified total of 6 cycles of obinutuzumab at the discretion of the treating physician. In addition, for patients that have surpassed the 24 cycles of CC-122, Celgene will continue to provide an additional 3 cycles of CC-122 to allow time for patients to be switched to commercially available therapies at the discretion of the treating physician.

Dosing of obinutuzumab is as described in the [GAZYVA](#) package insert or [GAZYVARO](#) SmPC.

Obinutuzumab will be administered as an IV infusion at a dose of 100 mg on Cycle 1 Day 1 and 900 mg on Cycle 1 Day 2 and 1000 mg on Cycle 1 Days 8 and 15. The dose of obinutuzumab on Days 1 and 2 of Cycle 1 may be adjusted per institutional practice as long as the combined dose equals 1000 mg. Obinutuzumab will be administered at a dose of 1000 mg on Day 1 of Cycles 2 through 6.

Obinutuzumab may be administered in either an inpatient or outpatient clinical setting. Full emergency resuscitation facilities must be immediately available in the event of a severe infusion reaction and subjects must be under close supervision of the investigator or appropriately trained staff during the infusions and the post-infusion period.

Please refer to the [GAZYVA](#) package insert or [GAZYVARO](#) SmPC for instructions for the preparation of each obinutuzumab dose. All transfer procedures during preparation require strict adherence to aseptic techniques. For microbiological stability, the diluted obinutuzumab

infusion solution should be used immediately. If not used immediately, the solution may be stored in a refrigerator at 2°C to 8°C (36°F to 46°F) for up to 24 hours prior to use.

Subjects will be premedicated prior to each infusion as described in Section 9.3.3.

Obinutuzumab will only be administered as a slow IV infusion through a dedicated line and **never as an IV push or bolus**. Infusion pumps should be used to control the infusion rate. Do not use an additional in-line filter because of the potential for adsorption. Infusion rates are outlined in [Table 10](#).

After the end of the first infusion, the IV line or central venous catheter should remain in place for \geq 2 hours to be able to administer IV treatments for infusion reactions if necessary. For subsequent infusions during Cycle 1, the IV line or central venous catheter should remain in place for at least 1 hour after the end of the infusion. For Cycles 2 and later, subjects who tolerate the infusion well without infusion reactions can have the IV line removed or the central venous catheter de-accessed immediately after the end of each infusion.

Table 10: Administered Dose and Infusion Rates for Obinutuzumab Infusions

Day of treatment cycle	Dose of obinutuzumab	Rate of infusion (in the absence of infusion reactions/hypersensitivity during previous infusions)
Cycle 1	Day 1	100 mg Administer at 25 mg/hr over 4 hours. Do not increase the infusion rate.
	Day 2	900 mg Administer at 50 mg/hr. The rate of infusion can be escalated in increments of 50 mg/hr every 30 minutes to a maximum rate of 400 mg/hr.
	Day 8	1000 mg Infusions can be started at a rate of 100 mg/hr and increased by 100 mg/hr increments every 30 minutes to a maximum of 400 mg/hr.
	Day 15	1000 mg
Cycles 2-6	Day 1	1000 mg

Please refer to [Table 14](#) for instructions on how to modify the dose in the event of an infusion reaction.

8.2.3. Dose Expansion Phase (Arms B and C only)

As of 05 Jul 2018, Phase 2 will not proceed.

When the Dose Escalation Phase is fully enrolled, and the evaluation completed, the preliminary RP2Ds for CC-122 in combination with ibrutinib and CC-122 in combination with obinutuzumab will be established for possible further evaluation of safety and preliminary efficacy in the Expansion Phase of the study.

Expansion cohorts at the RP2D may be conducted with a futility interim analyses as outlined in Section 10.3.1 and as shown below ([Table 11](#) and [Table 12](#)).

Table 11: Expansion Cohort: Arm B (CC-122 in Combination with Ibrutinib)

Expansion cohort	Population ^a	N
1	Treatment-naïve, ibrutinib-naïve, and high risk CLL subjects	Futility Interim: 6 Total: 10
	R/R, ibrutinib-naïve, and high-risk CLL subjects	Futility Interim: 16 Total: 40

^a Subjects must meet all other criteria for study entry.

Table 12: Expansion Cohort: Arm C (CC-122 in Combination with Obinutuzumab)

Expansion cohort	Population ^a	N
2	BCR PI or venetoclax resistant or intolerant subjects	Futility Interim: 17 Total: 40

^a Subjects must meet all other criteria for study entry.

Each subject will remain on the study until disease progression, unacceptable toxicity or treatment discontinuation for any other reason. A subject may discontinue one of the study treatments and remain on study with the other treatment in compliance with all study requirements if in the judgment of the investigator the subject will derive benefit from continued study treatment. Subjects who achieve MRD negativity (in both peripheral blood and bone marrow) lasting for a minimum of 3 months in duration have the option to discontinue study treatment; study treatment in these subjects may be resumed at the time of MRD positivity (see Section 4.1).

8.2.4. Definition of Stopping Criteria for Expansion Cohort

If at any time the early DLT rate (first 28 days of CC-122 dosing during CC-122 combination therapy) exceeds 20% or the late toxicity rate (AEs identified during the first 6 cycles of CC-122 dosing necessitating dose reduction or discontinuation that are clearly not related to disease progression, medical procedure, or intercurrent illness) exceeds 33%, enrollment to that expansion cohort will be suspended pending evaluation of the safety by the SRC. The SRC may reopen enrollment into that cohort at a lower dose level that has shown to be tolerated during the dose escalation portion of the study.

In addition, an interim analysis will be performed for each expansion cohort as outlined in Section 10.3.1. If criteria as specified are not met at the time of interim analysis, enrollment to that cohort will be stopped.

8.2.5. Definition of Not Tolerated Dose (NTD)

A dose level will be considered NTD when ≥ 2 out of 6 DLT evaluable subjects in a fixed-dose cohort experience an IP-related DLT.

8.2.6. Definition of Maximum Tolerated Dose (MTD)

The MTD is defined as the last dose level below the NTD with ≤ 1 out of 6 DLT evaluable subjects experiencing DLT during the DLT evaluation period.

8.2.7. Definition of Dose Limiting Toxicity (DLT)

National Cancer Institute CTCAE Version 4.03 are used as a guide for the grading of severity of adverse events (except as otherwise specified). Dose-limiting toxicities are described below:

- A non-hematologic AE that is clearly not related to disease progression, medical procedure or intercurrent illness and that commences within 28 days of first CC-122 dose and is \geq Grade 3 EXCEPT for:
 - Alopecia
 - Grade 3 rash of the acneiform or maculopapular type of not more than 4 days durations (with optimal medical management)
 - Grade 3 diarrhea or vomiting lasting less than 72 hours (with optimal medical management)
 - Grade 3 diarrhea requiring hospitalization and Grade 3 nausea or vomiting that required tube feeding, total parenteral nutrition, or hospitalization will be considered DLTs
- Tumor lysis syndrome (TLS), unless TLS does not progress to Grade 2 and resolves in less than 7 days with medical management
- \geq Grade 3 tumor flare reaction (per NCI CTC AE Version 3.0)
- Laboratory abnormality that is clearly not related to disease progression, medical procedure or intercurrent illness and that commences within 28 days of first dose of CC-122 and is \geq Grade 3 (unless otherwise specified below)
- Hematological toxicities as follows (grading as per IWCLL criteria):
 - Any febrile neutropenia
 - Grade 4 neutropenia lasting > 7 days
 - Any Grade 3 or 4 thrombocytopenia with clinically significant bleeding
 - Any cytopenia that requires dose reduction during the DLT evaluation period
- Grade 4 liver function tests or Grade 3 ALT with Grade 2 or higher bilirubin will be considered a DLT irrespective of underlying attribution
- Any AE assessed as clearly not related to disease progression, medical procedure or intercurrent illness and necessitating dose-level reduction during the DLT evaluation period.

8.2.8. Guidelines for Intrasubject Dose Escalation – Arm A

For Arm A, intrasubject dose escalation of CC-122 is permitted every 2 weeks at 0.5 mg increments at the discretion of the investigator as tolerated. Dose escalation may occur every 2 weeks if:

- The ANC is ≥ 1500 cells/mm³ ($1.5 \times 10^9/L$) or ≥ 1000 cells/mm³ ($1.0 \times 10^9/L$) if secondary to bone marrow involvement by disease
- The platelet count is $\geq 100,000$ cells/mm³ ($100 \times 10^9/L$) or $\geq 50,000$ cells/mm³ ($50 \times 10^9/L$) if secondary to bone marrow involvement by disease
- Any IP-related AE not requiring discontinuation has resolved to \leq Grade 1 severity or baseline
- AST/ALT is $< 3x$ ULN and total bilirubin is $< 1.5x$ ULN
- Subject does not meet any other criteria for dose reduction or modification

During the every 2 week dose escalation visit, the following safety assessments will include but are not limited to:

- Hematology
- Chemistry
- Vital signs
- Tumor Flare and Tumor Lysis Monitoring
- Adverse Event and Concomitant Medication Reporting
- CC-122 Contraceptive and Risk Counseling and Education (requirement at each CC-122 dispensation visit)

[figure not shown]
8.2.9. Dose Interruptions/Modifications

Dose modifications are permitted in any cycle, including Cycle 1 and the DLT evaluation period:

- Dose reductions that occur during the DLT evaluation period will constitute a DLT, but subjects will be allowed to continue on IP at a reduced dose.
- Dose reductions are allowed for CC-122 and ibrutinib. No dose reduction is allowed for obinutuzumab, but treatment may be discontinued at the discretion of the investigator for severe infusion or allergic reactions.

8.2.9.1. General Dose Modification Guidelines

Subjects will be evaluated for AEs at each visit with the NCI CTCAE (version 4.03) used as a guide for the grading of severity, with the exception of tumor flare (NCI CTCAE version 3.0), [REDACTED] and laboratory abnormalities as recommended by the IWCLL guidelines for the diagnosis and treatment of chronic lymphocytic leukemia [REDACTED] as listed below:

Subjects experiencing related AEs or SAEs \geq Grade 3 must interrupt dosing of the responsible IP or both IPs until resolution of the toxicity to \leq Grade 1 or baseline severity unless as otherwise indicated in [Table 14](#). If IP-related events do not resolve to \leq Grade 1 or baseline severity within 28 days despite adequate medical management, the sponsor's study medical monitor should be notified.

The dose of CC-122 may be reduced successively by one level from the starting dose. There will be no more than one dose level reduction from one cycle to the next unless otherwise permitted after consultation with the sponsor medical monitor. In addition, if a subject continues to experience unacceptable toxicity after two dose reductions (with the exception of CC-122 per [Table 15](#) where up to 3 dose reductions may be allowed for selected doses), IP will be discontinued permanently. If a dose is reduced for toxicity other than a Grade 4 non-hematological toxicity, re-escalation is permitted after the toxicity is resolved. If the toxicity recurs after re-escalation, the subject should remain at the lower dose level. Subjects who experience a Grade 4 non-hematological toxicity may not have their dose re-escalated.

For the combination of CC-122 and ibrutinib or obinutuzumab, in the event of a toxicity requiring dose modification, CC-122 should be considered for interruption and dose reduction first if possible. If the subject continues to require dose modification after a dose hold and/or reduction of CC-122 a dose interruption of obinutuzumab or ibrutinib or reduction of ibrutinib may be considered.

Dose interruptions lasting beyond 28 days should be discussed with the sponsor's study medical monitor.

If it becomes necessary to permanently stop administration of one of the IPs, continuation on the other IP will require discussion and agreement between the sponsor's study medical monitor and the investigator.

8.2.9.2. Dose Modification Guidelines

Any IP-related toxicity meeting the definition of DLT will require dose reduction or interruption. The criteria for dose reduction are listed in [Table 14](#), should be used for dose modifications.

Chronic Grade 2 toxicity (other than specified below) may warrant dose reduction or interruption of one or both IP. Such cases should be discussed with the sponsor's medical monitor before changes are made.

Dose modification decisions for patients with cytopenia (below the lower limit of the normal range) at **baseline** will be based on the IWCLL guideline ([Table 13](#)). For patients with a normal neutrophil count, platelet count and/or hemoglobin value at baseline, the NCI CTCAE (version 4.03) will be used.

Any dose modifications must be recorded on the respective Study Drug Record eCRF.

Table 14: Dose Reduction Guidelines

Adverse Event	Grade	Action	Agent to be considered for interruption/reduction (in descending order)
Thrombocytopenia	≥ Grade 3	
• Hold all IP• Follow CBC at least every 7 days• If thrombocytopenia resolves to ≤ Grade 2, restart IP and reduce CC-122 to the next lower dose level. Ibrutinib may be restarted after thrombocytopenia resolves to ≤ Grade 1 or baseline at original dose after the 1st occurrence, and reduce by one dose level at each subsequent recurrence with a maximum of 2 dose reductions allowed. A 4th recurrence requires permanent discontinuation of ibrutinib.• Obinutuzumab should be restarted at the full dose after thrombocytopenia resolves to ≤ Grade 2, no dose reduction is allowed.	
• CC-122• Ibrutinib/obinutuzumab

Table 14: Dose Reduction Guidelines (Continued)

Adverse Event	Grade	Action	Agent to be considered for interruption/reduction (in descending order)
Neutropenia	\geq Grade 3 with infection OR Sustained (\geq 7 days) Grade 3 OR \geq Grade 3 associated with fever (temperature \geq 38.5°C) OR Grade 4	
 Hold all IP Follow CBC at least every 7 days If neutropenia resolves to \leq Grade 2, restart IP at the same or reduced dose level at the investigator's discretion (restarting at the same dose level is permitted only one time for those subjects with Grade 4 neutropenia. If Grade 4 neutropenia recurs, the IP dose must be reduced upon resolution). Ibrutinib may be restarted after neutropenia resolves to \leq Grade 1 or baseline at original dose (420 mg per day) after the 1st occurrence, and reduce by one dose level (to 280 mg per day) at each subsequent recurrence with a maximum of 2 dose reductions (to 140 mg per day) allowed. A 4th recurrence requires permanent discontinuation of ibrutinib. Obinutuzumab should be restarted at the full dose after neutropenia resolves to \leq Grade 2, no dose reduction is allowed. Use of growth factors (G-CSF, GM-CSF) is permitted at the discretion of the investigator 	
 CC-122 Ibrutinib/obinutuzumab
Troponin-T/BNP	Troponin-T > ULN with associated significant elevation in BNP or with cardiac symptoms or significant changes in ECG or LVEF	
 Hold CC-122 Cardiology evaluation Follow troponin-T, BNP, and ECG at least every 7 days If troponin-T and BNP stabilize and there are no other significant cardiac findings, restart CC-122 at the same or next lower dose level Permanently discontinue CC-122 if Troponin-T > ULN with cardiac symptoms or significant changes in ECG or LVEF 
Please refer to Section 8.2.9.2.3 for additional guidance
	
 CC-122

Table 14: Dose Reduction Guidelines (Continued)

Adverse Event	Grade	Action	Agent to be considered for interruption/reduction (in descending order)
AST/ALT/ Bilirubin	≥ Grade 3	
 Hold one or more IPs at investigator's discretion Follow labs at least every 7 days If abnormalities resolve to ≤ Grade 1 or baseline, restart IPs and reduce CC-122 to the next lower dose level For ibrutinib, once the toxicity has resolved to Grade 1 or baseline (recovery), ibrutinib therapy may be reinitiated at the starting dose (420 mg per day). If the toxicity reoccurs, reduce dose to 280 mg per day. A second reduction of dose to 140 mg per day may be considered as needed. If these toxicities persist or recur following two dose reductions, discontinue ibrutinib. 	
 CC-122 Ibrutinib
	ALT and/or AST ≥ 3x ULN and total bilirubin > 2x ULN (potential Hy's Law)	
 Hold all IPs Conduct medical work up to determine the cause of abnormalities Follow labs at least every 7 days until resolution to ≤ Grade 1 or baseline severity for all AST, ALT and total bilirubin In case of confirmed Hy's Law, dosing will not be resumed 	
Stomatitis/Nausea/ Vomiting / Constipation	≥ Grade 3	
 Hold one or more IPs at investigator's discretion if AE fails to respond to symptomatic treatment When the toxicity resolves to ≤ Grade 1 or baseline restart both IP. For ibrutinib, once the toxicity has resolved to Grade 1 or baseline (recovery), ibrutinib therapy may be reinitiated at the starting dose (420 mg per day). If the toxicity reoccurs, reduce dose to 280 mg per day. A second reduction of dose to 140 mg per day may be considered as needed. If these toxicities persist or recur following two dose reductions, discontinue ibrutinib. 	
 CC-122 Ibrutinib

Table 14: Dose Reduction Guidelines (Continued)

Adverse Event	Grade	Action	Agent to be considered for interruption/reduction (in descending order)
Diarrhea	≥ Grade 3	
 Hold one or more IPs at the investigator's discretion Strongly recommend to perform a colonoscopy and biopsy When the toxicity resolves to ≤ Grade 1 restart IPs and reduce CC-122 to the next lower dose level. For ibrutinib, once the toxicity has resolved to Grade 1 or baseline (recovery), ibrutinib therapy may be reinitiated at the starting dose (420 mg per day). If the toxicity reoccurs, reduce dose to 280 mg per day. A second reduction of dose to 140 mg per day may be considered as needed. If these toxicities persist or recur following two dose reductions, discontinue ibrutinib. 	
 CC-122 Ibrutinib
Rash	≥ Grade 3	
 Discontinue suspected IP for desquamating (blistering) Grade 3 or any Grade 4 rash For maculopapular, acneiform, or pustular rashes lasting ≤ 7 days medical management is warranted 	
 CC-122 Ibrutinib
Allergic Reaction or Hypersensitivity	≥ Grade 3	
 For obinutuzumab: Grade 3: premedicate future doses and adjust infusion rates per standard practice Recurring Grade 3 or Grade 4: permanently discontinue CC-122 or ibrutinib, discontinue one or more suspected IPs 	
 Obinutuzumab CC-122 Ibrutinib
Venous Thrombosis / Embolism	≥ Grade 3	
 Hold CC-122 at investigator's discretion and start anticoagulation; restart CC-122 at investigator's discretion (maintain dose level) Discontinue ibrutinib 	
 CC-122 Ibrutinib
Peripheral Neuropathy (applies only to those neuropathies which begin or worsen while on study)	Newly developed ≥ Grade 3	
 Hold CC-122 at investigator's discretion When the toxicity resolves to ≤ Grade 2 or to baseline, restart CC-122 at the next lower dose level 	
 CC-122

Table 14: Dose Reduction Guidelines (Continued)

Adverse Event	Grade	Action	Agent to be considered for interruption/reduction (in descending order)
Bleeding Events	≥ Grade 2	
 Hold one or more IPs at investigator's discretion When the toxicity resolves to ≤ Grade 1, restart one or more IPs 	
 Ibrutinib CC-122
Tumor Lysis Syndrome	Laboratory or Grade 1 TLS	
 Continue treatment at same dose level or one dose level dose reduction Provide vigorous intravenous hydration and appropriate medical management according to the local standard of care, until correction of electrolyte abnormalities. Treat appropriately as needed to reduce hyperuricemia Hospitalization will be at investigator's discretion 	
 CC-122 Ibrutinib/obinutuzumab
	Grade 2-4	
 Hold CC-122 and ibrutinib/obinutuzumab When symptoms resolve to Grade 0, restart IPs at the next lower dose level (CC-122 and ibrutinib) or full dose (obinutuzumab). If IPs resumed prior to the start of a subsequent cycle, a chemistry test should be performed every other day for the first week following re-initiation of IPs 	
Tumor Flare Reaction (TFR)* *assessed according to NCI CTCAE Version 3.0	Grades 1-2	
 Continue CC-122, maintain dose level Initiate therapy with corticosteroids at the investigator's discretion NSAIDs and/or narcotics may also be used as per investigator's discretion 	
 CC-122
	Grades 3-4	
 Hold CC-122 Initiate therapy with corticosteroids NSAIDs and/or narcotics may also be used per investigator's discretion When symptoms resolve ≤ Grade 1, restart CC-122 at the same dose level 	
Other	≥ Grade 3	
 Hold one or more IPs at investigator's discretion When the toxicity resolves to ≤ Grade 2, restart both IPs and reduce CC-122 to the next lower dose level. Refer to package inserts or SmPCs for the approved products for dose modification instructions (ibrutinib and obinutuzumab). 	--

Table 14: Dose Reduction Guidelines (Continued)

Adverse Event	Grade	Action	Agent to be considered for interruption/reduction (in descending order)
Renal and urinary	CrCl decreased from ≥ 50 mL/min to 30-49 mL/min and 30% drop from baseline	
 Decrease dose to next dose level 	
 CC-122
	CrCl decrease to < 30 mL/min	
 Hold CC-122 When CrCl improves to ≥ 30 mL/min, restart CC-122 at the next lower dose level 	
 CC-122
Surgical Procedures	Minor	
 Hold one or more IPs at investigator's discretion on day of surgery IPs may be restarted at same dose level upon recovery 	
 Ibrutinib CC-122
	Major	
 Hold one or more IPs for 3 to 7 days prior to surgery through 3 to 7 days post surgery Restart IPs upon recovery and at least 3 to 7 days post surgery at the same dose level 	
Infusion Reaction	Grade 1-2	
 Reduce infusion rate ($\leq 50\%$ prior rate) or interrupt infusion and treat symptoms Upon resolution, continue or resume infusion; infusion rate increments and intervals may resume at the increments and intervals as appropriate for the treatment dose if no further infusion reaction symptoms 	
 Obinutuzumab
	Grade 3 (severe) infusion reaction	
 Interrupt infusion and manage symptoms Upon resolution, restart infusion at $\leq 50\%$ prior rate; infusion rate escalations can resume at the increments and intervals as appropriate for the treatment dose if no further infusion reaction symptoms Permanently discontinue if Grade 3 or higher infusion-related symptom occurs with re-challenge 	
	Grade 4 (life threatening) infusion reaction	
 Stop infusion immediately; permanently discontinue 	

Table 14: Dose Reduction Guidelines (Continued)

Adverse Event	Grade	Action	Agent to be considered for interruption/reduction (in descending order)
Progressive Multifocal Leukoencephalopathy	All	
 Permanently discontinue 	
 Obinutuzumab
Pneumonitis	Grade 2	
 Hold one or more IPs at investigator's discretion Once symptoms have resolved completely, CC-122 and/or ibrutinib may be restarted at the next lower dose level. 	
 CC-122 Ibrutinib
	≥ Grade 3	
 Discontinue one or more suspected IPs permanently 	
Atrial Fibrillation	Grade 3 or 4 or persistent atrial fibrillation of any grade	
 Consider the risks and benefits of ibrutinib treatment. If clinically indicated, the use of non-prohibited anticoagulants or antiplatelet agents may be considered for the thromboprophylaxis of atrial fibrillation. If dose of ibrutinib is reduced, at the investigator's discretion, the dose of ibrutinib may be escalated after 2 cycles of a dose reduction in the absence of a recurrence of the toxicity that led to the reduction. 	
 Ibrutinib

Abbreviations: BNP = B-type Natriuretic Peptide; CBC = Complete Blood Count; CrCl = Creatinine Clearance; ECG = Electrocardiogram; G-CSF = Granulocyte Colony-Stimulating Factor; GM-CSF = Granulocyte-Macrophage Colony-Stimulating Factor; IP = Investigational Product; LVEF = Left Ventricular Ejection Fraction; NSAID = Non-steroidal Anti-inflammatory Drug; TLS = Tumor Lysis Syndrome; ULN = Upper Limit Normal.

The image consists of a series of horizontal bands. The bands are primarily black, with thin white horizontal lines separating them. The image is heavily pixelated and appears to be a scan of a document or a specific type of data visualization. The overall effect is a high-contrast, binary-like pattern.

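### Followed as written, Table 14's thrombocytopenia and neutropenia rows leave a fourth event with neither an ibrutinib restart dose nor a stop

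*Protocol*

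**What the plan says.** Table 14 in Protocol Section 8.2.9.2 is the operative table for dose modification. In its thrombocytopenia row, each qualifying event leads to a hold of all study drugs. After recovery, ibrutinib may resume at its original dose following the first occurrence; after that the instruction is to "reduce by one dose level at each subsequent recurrence with a maximum of 2 dose reductions allowed". The neutropenia row has the same structure and adds the doses: 420 mg, then 280 mg, "with a maximum of 2 dose reductions (to 140 mg per day) allowed". Both rows close with the same sentence: "A 4th recurrence requires permanent discontinuation of ibrutinib". The neutropenia row also says, of study drug in general: "If Grade 4 neutropenia recurs, the IP dose must be reduced upon resolution".

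Section 8.2.9.1 sets a general rule: "if a subject continues to experience unacceptable toxicity after two dose reductions", then "IP will be discontinued permanently". The only exception named is for CC-122, where Table 15 allows a third reduction at some doses. The same section says that in the combinations "CC-122 should be considered for interruption and dose reduction first if possible". It also says that after a reduction for anything other than a Grade 4 non-hematologic toxicity, "re-escalation is permitted after the toxicity is resolved".

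Three other rows of Table 14 carry an ibrutinib ladder: AST/ALT/bilirubin; stomatitis/nausea/vomiting/constipation; and diarrhea. Each stops ibrutinib when the toxicity persists or returns after two reductions, although the second reduction is optional there. Table 16 (Section 8.2.12.2) steps through 420, 280 and 140 mg and stops at the fourth occurrence, but it is headed as covering non-hematologic events.

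**The concern.** The two cytopenia rows use *occurrence* for the first event and *recurrence* for later ones. Read that way, a fourth recurrence is the fifth event, but the ladder in the same row runs out of permitted reductions at the third. At the fourth event the row tells the site to hold treatment and follow the blood count. It then calls for a reduction that its own cap rules out, and does not yet require a stop.

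This is a safety stopping rule still in force under Amendment 7 for subjects continuing on ibrutinib: Arm B, and any Arm A subject who added ibrutinib after progression. A site facing a fourth Grade 3 or higher thrombocytopenia, or a fourth qualifying neutropenia, has to look outside the row to learn whether ibrutinib ends, while the row's own sentence puts the mandatory stop one event later. Practice could differ between sites.

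**Working it through.** No sample-size or error-rate calculation applies; the check is a count along the ladder.

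Inputs:
- First event: restart at the original dose, no reduction used (both rows).
- Each later event: one level down, maximum two reductions (both rows). The levels are 280 and 140 mg (neutropenia row; the same levels appear in Table 16).
- Mandatory stop: fourth recurrence (both rows).
- Recurrence *k* is event *k* + 1, so the stated stop is event 4 + 1 = 5.

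| Event | Row as written, no re-escalation | One reduction deferred (CC-122 reduced first) |
|---|---|---|
| 1 | 420 mg | 420 mg |
| 2 (recurrence 1) | 280 mg | 420 mg |
| 3 (recurrence 2) | 140 mg, both reductions used | 280 mg |
| 4 (recurrence 3) | hold; no restart dose, no stop | 140 mg, both reductions used |
| 5 (recurrence 4) | stop | stop |

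Let *d* be the number of recurrences at which ibrutinib makes no net step down, because the reduction was deferred or was later reversed by re-escalation. Reductions are counted as levels below 420 mg.

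- Both reductions are used by event 3 + *d*.
- The first event with none left is 4 + *d*.
- Lag of the row's stop = 5 − (4 + *d*) = 1 − *d*.

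Results:
- *d* = 0: lag 1.
- *d* = 1: lag 0. The deferral column is one such path. Re-escalation gives another: 420 mg; 280 mg then back to 420 mg; 280 mg; 140 mg; stop.
- *d* = 2: lag −1. The doses are 420, 420, 420 and 280 mg, and the stop at event 5 comes with one reduction still unused.

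The lag is therefore one event at most. A fixed event count can also stop ibrutinib too early.

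Comparison with the other rules, for *d* = 0:
- Section 8.2.9.1: stop if unacceptable toxicity continues after two reductions, so event 4 at the earliest. The trigger is a clinical judgement, not a count.
- The three other Table 14 rows: stop on return after two reductions, so event 4 if both reductions were taken.
- Table 16: stop at event 4. Sections 8.2.2.2 and 8.2.12 point to it for ibrutinib without a non-hematologic limit, but its own heading has that limit, so it supports the point by analogy only.

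Testing a one-word change from *recurrence* to *occurrence*: with *d* = 0 it gives 420, 280, 140 mg, stop, which leaves no gap. With *d* = 1 it gives 420, 420, 280 mg, stop at event 4, and the permitted 140 mg step is lost.

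**The case against.** The strongest reply is that the documents can be read together without conflict. The sentence makes discontinuation mandatory by a certain point and does not forbid stopping sooner. Section 8.2.9.1 already ends treatment when unacceptable toxicity continues after two reductions, and its only exception is for CC-122. Restart of ibrutinib is permissive throughout. The one-event gap needs a reduction at every recurrence and no re-escalation, whereas Section 8.2.9.1 puts CC-122 first and allows re-escalation. The other ladders used for comparison are all for non-hematologic toxicity.

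Much of this stands. A reader might infer that ibrutinib may not be stopped before the fifth event; the text does not say that. A reader might also infer that the rows authorise another restart at 140 mg after the fourth event. No row says so, the rows call for a step down at each recurrence, and for recurrent Grade 4 neutropenia a same-dose restart sits badly with the required reduction.

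The reply does not close the gap. The general rule turns on judgement, while the row gives a number, and Section 8.2.9.2 directs sites to Table 14 for the criteria. At event 4 on the row's own ladder, the row still gives neither a dose nor a stop.

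**Conclusion.** The inconsistency is real and minor. With ibrutinib reduced at each recurrence and not re-escalated, the mandatory stop comes one event after the permitted reductions run out. With one reduction deferred or reversed, the gap is zero. Section 8.2.9.1 points to the earlier stop but does not fully supply it, because its trigger is not an event count.

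A reader might conclude that the sentence is simply a slip for the fourth occurrence. That is plausible, since it would reproduce the Table 16 ladder, but the documents do not establish intent, and the point does not depend on it.

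Nor do the documents support any wider effect. The number of subjects reaching a fourth qualifying cytopenia cannot be derived from them. It is likely to be small: enrolment closed on 05 Jul 2018, Arm B was planned at 24 (18 to 36) subjects in dose escalation, and ibrutinib restarts only after recovery to Grade 1 or baseline. No DLT, MTD or statistical result changes.

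**What to change.** By clarification letter, replace the closing ibrutinib sentence in both the thrombocytopenia and the neutropenia rows of Table 14 with:

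*If the toxicity recurs following two ibrutinib dose reductions (ie, the 4th occurrence when ibrutinib is reduced at each recurrence), permanently discontinue ibrutinib.*

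This gives 420, 280, 140 mg, then stop, on the path as written. It keeps the 140 mg step when a reduction has been deferred, and it matches Section 8.2.9.1 and the other ibrutinib rows of Table 14. The cost is one sentence in two rows, with no new data, visits or analyses.
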